1. BACKGROUND

Approximately 8,500 Veterans with transient ischemic attack (TIA) or stroke are cared for in a Department of Veterans Affairs (VA) Emergency Department (ED) or inpatient ward annually.¹ Patients with transient ischemic attack (TIA) are at very high risk of recurrent vascular events; over the long-term 11% per year will have a stroke, myocardial infarction or vascular death.²⁻⁴ Because patients with TIA and minor stroke have little neurological impairment yet are at high risk of recurrent events, including disabling stroke, they are ideal candidates for interventions to reduce their risk of adverse events. Several studies have demonstrated that interventions which deliver timely care reduce the risk of recurrent vascular events by 70%.⁵

Our group has assessed the quality of care for Veterans with TIA and minor stroke cared nationwide and has found considerable gaps in care quality (e.g., 51% of eligible Veterans receive carotid imaging, 27% receive indicated antihypertensive medication intensification).⁶ In other words, Veterans are not receiving the timely, guideline concordant care they need to prevent recurrent vascular events. The objective of the PREVENT project is to develop and evaluate an intervention program to improve the quality of care for Veterans with TIA and minor stroke.

2. SPECIFIC AIMS

Aim 1. To develop a program to improve the care of Veterans with TIA or minor stroke that can be deployed nationwide. The program includes 5 components: (1) a reporting system that is based on validated electronic quality measures that allow staff to monitor the time-sensitive processes of care and outcomes of their Veterans with TIA; (2) clinical programs based on existing VHA infrastructure (e.g., a pharmacist-based TIA medication management program); (3) a staff education and training program; (4) protocols and templates for use by clinicians, nurses and pharmacists; and (5) quality improvement support including a virtual collaborative to share lessons learned across sites. We will measure users' assessment of the PREVENT program in terms of usability, complexity, and relative advantage to deliver and improve care to Veterans with a recent TIA or minor stroke. We hypothesize that we can develop and facilitate the implementation of a program to improve guideline concordant care for Veterans with a recent TIA or minor stroke that achieves a high degree of staff satisfaction.

Aim 2. To evaluate the effectiveness of an intervention program for Veterans with TIA or minor stroke against usual care. Teams at the 6 intervention sites will be given access to the intervention program in 3 waves of 2 sites per wave. The primary effectiveness outcome is the proportion of Veterans who received all of the guideline-concordant processes of care for which they are eligible referred to as the "Without-Fail" care rate. We will compare the Without-Fail

rate observed in the post-implementation phase to the baseline period. We hypothesize that the Without-Fail care rate will be improved by the intervention program.

Aim 3. To evaluate the implementation of the intervention program across the 6 participating sites. The two primary implementation outcomes will be the number of implementation activities completed during the one-year active implementation period and the final level of team organization (defined as the Group Organization (GO Score)) for providing and improving TIA care at the end of the 12-month active implementation period. A covariate will include the degree of participation [Total # of calls attended/12 active implementation calls] in the monthly collaborative calls as noted in the call attendance. Implementation activities completed will be identified from multiple data sources: key updates and topics discussed during the collaborative calls; monthly action plan achievements and additional facilitator notes; the HUB implementation plan updates; and 6 and 12-month interviews. We hypothesize that sites that engage in ongoing [positive] implementation strategies of reflecting and evaluating, goal setting, and planning will realize the greatest implementation success (defined across the two primary implementation outcomes: number of implementation activities and the Group Organization (GO score)). We also hypothesize that sites with greatest implementation success will achieve the highest Without-Fail rate. We further plan to map implementation activities completed onto the key implementation strategies (reflecting and evaluating, goal setting, and planning) stratified by valence [positive & negative] based upon the mixed methodology coding.

Secondary Aim To evaluate the sustainability of the program. Sustainability will be evaluated over a one-year period that begins after the one-year active implementation period. We will compare the Without-Fail rate in the sustainability period to the post-implementation period. Our hypothesis is that sites that implement a facility-wide, TIA System of Care (reflected in a final 12-month GO score between 8-10) will demonstrate the greatest program sustainability as measured by the Without-Fail rate. Further, sites that maintain their implementation activities involving PREVENT-related program elements during the sustainability period will demonstrate the greatest program sustainability as measured by the Without-Fail rate.

3. RATIONALE

Imperative to Provide Timely Care for Patients with TIA and Minor Stroke. Because the risk of recurrent vascular events is highest early after an index cerebrovascular event,⁴ preventive actions must be applied early to maximize the benefit. Several non-VA studies have demonstrated improved outcomes for TIA/minor stroke patients with programs that emphasize early evaluation and management including: lower stroke rate, reduced lengths of hospital stay, reduced costs, and improved vascular risk factor management.⁷⁻⁹ The EXPRESS study demonstrated that early assessment and management of TIA/minor stroke patients reduced the 90-day stroke risk by 80% (from 10.3% to 2.1%).⁹ Similarly, the SOS-TIA study, found a 79% reduction in the 90-days stroke rate (from a predicted rate of 5.96% to an observed rate of 1.24%).¹⁰ The FASTEST¹¹ trial demonstrated that an electronic protocol for use in general practice improved care and outcomes for patients at lower cost than usual care; guideline adherence improved from 41% to 76% and the 90-day recurrent vascular event rate decreased from 11.9% to 3.5%.¹¹ FASTEST is particularly relevant because it integrated care across settings and was designed to improve care for patients with limited access to specialists.¹¹

Strength of the Evidence Supporting the Intervention. Substantial evidence exists related to the design of our proposed intervention and the focus on specific processes of care. First, FASTER, SOS-TIA and EXPRESS all included algorithms or protocols that facilitate the timely delivery of care. In addition, numerous studies have demonstrated that nurse-administered, telephone-delivered care can improve vascular risk factor control for Veterans.^{12,13} The planned

[figure not shown]
intervention similarly includes algorithms and protocols for the timely delivery of guideline concordant care. Finally, the processes of care that are the focus of the intervention are all supported by the AHA/ASA secondary prevention guidelines or other relevant professional organization guidelines.¹⁴ For each process in this project, evidence supports the association between the process of care and improved outcomes. Moreover, most of the processes were included in one of the prior trials that have demonstrated that protocol-based care dramatically reduces the risk of recurrent vascular events.^{11,15}

4. METHODS

4.1 Aim 1 Methods (Program Development)

The development of the PREVENT program was based on four main components: (1) interviews with VHA staff members involved in the care of patients with cerebrovascular disease;¹⁶ (2) validation of electronic quality measures against chart review for use in ongoing assessment of a broad range of processes of care at all VHA medical centers;¹⁷ (3) baseline quality of care data identifying potential gaps in care that should serve as targets for quality improvement;¹⁸ and (4) the existing literature regarding effective TIA clinical programs.^{11-13,15}

As part of a prior project,¹⁶ we met with diverse staff members involved in the care of patients with stroke and TIA including: stroke team members (which included nursing, neurology, and ED members), pharmacy, primary care providers, hospitalists, radiology, vascular surgery, cardiology, ophthalmology, systems redesign, and quality management staff. Based on interviews with these staff, we identified barriers to providing high quality TIA care including:

which were successfully deployed in prior TIA intervention studies.

PREVENT Intervention Components Description

The PREVENT QI program includes 5 components: (1) a reporting system that is based on validated electronic quality measures that allow staff to monitor the time-sensitive processes of

care and outcomes of their Veterans with TIA; (2) clinical programs based on existing VHA infrastructure (e.g., a pharmacist-based TIA medication management program); (3) a staff training program; (4) protocols and templates for use by clinicians, nurses and pharmacists; and (5) quality improvement support including a virtual collaborative to share lessons learned across sites.

Implementation Strategies

The PREVENT program employs three primary implementation strategies: (1) team activation via (a) audit and feedback, (b) reflecting and evaluating, (c) planning, and (d) goal setting; (2) external facilitation; and (3) building a community of practice. In addition, PREVENT allows for local adaptation of the intervention and also takes advantage of peer pressure while providing facilitation support to the site champion. During the active implementation period, we are tracking the adopted and adapted PREVENT program elements chosen by each site across the waves. Adoption is defined as PREVENT program elements chosen to be implemented at a local site. Adaptation is defined as site specific modifications made to the chosen PREVENT program elements during implementation.

Aim 1 Evaluation

Our assessment of the program development is based on the end-user evaluation of the usability, and complexity of the program to deliver and to improve care to Veterans with TIA.¹⁹ We will obtain these data during interviews conducted 6-months after the start of active implementation and again at the end of active implementation.

Aim 1 Assessments: staff satisfaction with the intervention Obtained at 6-months and 1-year after the start of active implementation
Participant perceptions and overall experience with each of the following elements of PREVENT as well as: the ease of use, how useful each element is to providing or improving care, and whether they are using each element: 
1. PREVENT overall2. The five components3. Kick-Off4. Hub (overall perceptions, usability, how are they using the hub)5. Virtual collaborative/monthly calls6. External facilitation
Participant perceptions of PREVENT program complexity and usability
Describe any sharing of tools with peers or with leadership at own facility, with other facilities
Which components of PREVENT are the most helpful to you as you work to improve outcomes for your Veteran patients with TIA/minor stroke?
Specific quality improvement activities planned for next 6 months

Audience-response system (ARS) feedback about program components and staff written evaluations obtained during the Kick-Off will also inform the assessment of staff satisfaction with the intervention and implementation strategies.

Aim 1 Analysis

Aim 1 Hypothesis: that we can develop a program to improve guideline concordant care for Veterans with a recent TIA or minor stroke that achieves a high degree of staff satisfaction

(defined as users' assessment of the PREVENT program in terms of usability, complexity, and relative advantage to deliver and improve care to Veterans with a recent TIA or minor stroke).

The assessment of staff satisfaction with the PREVENT program and its components will utilize mixed methods. We will seek to identify the components of the intervention that were considered to be most useful and/or most important to the local PREVENT program in both the 6-and 12-month interviews as well as the staff program evaluations completed at the end of the day long site kick off.

Interviews with facility stakeholders will be conducted in person during site visits or by telephone. Key stakeholders are defined as front line staff, managers, and leadership affiliated with the delivery of TIA care. We will also accept "snowball" referrals from key stakeholders. Upon receipt of verbal consent, all interviews will be audio recorded. The audio recordings will be transcribed verbatim. All transcripts will be de-identified and imported into an Nvivo11 project file for data coding and analysis. Project team members will independently read and code identical transcripts using a common codebook derived from the semi-structured interview guide and project analysis plan. We plan to code for the presence or absence of constructs as well as the magnitude and valence each specified Consolidated Framework for Implementation Research (CFIR) constructs. Each coded transcript will be merged into a single file, and the project team will meet as a group to review and discuss similarities and differences in the coding selections until a shared understanding of each item in the codebook had been developed. All codes will be defined with examples in a common codebook and updated as needed by team agreements on modifications. At a minimum, two coders per interview will be assigned to each interview to best capture the specified constructs. Completed coded interviews from each site will be merged into Facility level estates and ultimately, all Facility level estates will be merged into a Project Universe file for analysis.

Coding for Usability and Complexity. We will derive the users' assessment of the intervention using the Intervention Characteristics domain from the Consolidated Framework for Implementation Research (CFIR). We will code statements on the presence of Intervention specific CFIR constructs about how the PREVENT program was useful for their local adopted program to delivery TIA care as well as statements on how it was not helpful; we will code statements about how complex the PREVENT program components were to implement as well as statements on the lack of complexity/ease of the components' implementation to improve the 7-key metrics of TIA related care.

Coding for Context. We will continue to use the CFIR coding methodology to denote the presence or absence of the local context including the following from the inner setting: structural characteristics, networks and communications, culture, learning climate, leadership engagement, and available resources as well as champions in the implementation process.

[figure not shown]
Key Implementation Strategies and CFIR constructs. We will expand the CFIR coding to include valence (positive + and negative -) influences on implementation for our key implementation strategies: reflecting and evaluation; goal setting and feedback; planning; and champions.

4.2 Aim 2 Methods (Effectiveness)

Design

This five-year stepped-wedge^{20,21} evaluation includes a total of 6 sites, where active implementation is initiated in 3 waves each of which includes 2 sites. The project involves three

[figure not shown]
phases at each of the six sites: a one year-baseline phase, a one-year active implementation phase, and a sustainability phase of at least one year in duration follows the end of active implementation.

Power and Sample Size

The six site, stepped wedge design provides >90% power to detect an improvement in the mean facility Without-Fail rate from 25% during the baseline data period to >50% during the active implementation data period. The goal for the sample size was to recruit sites with at least 50 TIA patients per year, however, power was preserved with at least 30 TIA patients per year.

The figures below provide the plots of the power calculated based on the modified formula for testing the intervention effect $H_0: \theta = 0, H_1: \theta = \theta^M$ for the intervention effect size θ^M ranging from 0.1 to 0.3 when taking account for a potential decrement in intervention effect over time γ . The plot was based on a total of 6 clusters with a cluster sample size of 30, 50 and 70, respectively. The results demonstrated that this variant of SWD generally has a reasonable power (greater than or equal to 0.90) for detecting the intervention effect when the effect size is at least 0.15 with a cluster size no less than 30. The coefficient of variation (CV) was set at 0.2, 0.4, 0.6, and 0.8 to cover a wide range of the between-hospital variation. The CV seemed to have little effect on power.

Site Selection

Sites were invited to participate on the basis the basis of demonstrated gaps in quality of care (identified using the validated eQMs). Specifically, sites were invited to participate if they had baseline without-fail rates of <50%. Invitations were sent via email to higher volume sites first and recruitment continued until 6 participating sites were identified. No minimum threshold on volume was employed because our goal was to include sites which were diverse so that the results might be widely generalizable across the full spectrum of VHA facilities.

Allocation of Sites to Waves

Although some stepped-wedge trials randomly assign facilities to waves, PREVENT sites were allocated to waves on the basis of the pragmatics of the ability to schedule baseline and Kick-Off meetings.

Intervention Implementation

The multi-faceted PREVENT intervention (described above) will be implemented via a Kick-Off meeting which includes all relevant staff members at participating sites and then through monthly telephone conference calls which include all members of the teams at the participating sites after the Kick-Off. Participants in the collaborative calls receive CME (Continuing Medical

Education) for clinicians and pharmacists or CEU (Continuing Education Units) for nurses. All data, quality improvement plans, professional education materials and other resources will be shared with the sites through the web-based portal, referred to as the PREVENT hub.

Focus on Staff/Facilities

The intervention targets participating site staff members. Individual patients are not the target of the intervention or the implementation activities.

Effectiveness Outcome: The Without-Fail Rate

The primary effectiveness outcome, referred to as the Without-Fail care rate, is the proportion of Veterans who received all of the care for which they are eligible from among 7 key processes of care: brain imaging, carotid artery imaging, neurology consultation, hypertension control, anticoagulation for atrial fibrillation, antithrombotics, and high/moderate potency statins. The Without-Fail rate is calculated at the facility level based on electronic health record data using validated algorithms.¹⁷ Data from all TIA patients cared for in the participating facilities' Emergency Departments (ED) or inpatient settings are included in the measurement of the without-fail rate.

Effectiveness Data Period Definitions

Sites	Baseline Data Period (Control Period)	Date of Baseline Site Visit	Pre-implementation Data Period	Date of Kick-Off	Post-Implementation Data Period	Sustainability Data Period
			Time between baseline visit and Kick-Off		1 year after Kick-Off: Months 2-13 after the Kick-Off	Variable period: Months 14 after the Kick-Off until 9/30/19
A	8/21/15-8/21/16	8/22-23/16	8/24/16-7/10/17	7/11/2017	8/11/17-8/10/18	8/11/18-9/30/19
B	8/29/15-8/29/16	8/30-9/1/16	9/2/16-7/25/17	7/26/2017	8/26/17-8/25/18	8/26/18-9/30/19
C	7/30/16-7/31/17	8/1-2/17	8/3/17-10/17/17	10/18/2017	11/18/17-11/17/18	11/18/18-9/30/19
D	6/12/16-6/12/17	6/13-14/17	6/15/17-11/1/17	11/2/2017	12/2/17-12/1/18	12/2/18-9/30/19
E	8/23/16-8/23/17	8/24-25/17	8/26/17-12/6/17	12/7/2017	1/7/18-1/6/19	1/7/19-9/30/19
F	1/30/2017-1/30/2018	1/31-2/1/18	2/2/2018-4/12/2018	4/13/18	5/13/18-5/12/19	5/13/19-9/30/19

Primary Aim 2 Analysis:

Descriptive Analysis: The Without-Fail care rate will be estimated at each site for each of the three periods (baseline, post-implementation, and sustainability) to exam the temporal trends in the intervention effectiveness. The 95% confidence intervals for the rates will be provided.

Statistical Models: Due to the variation of sample size across the sites and across the implementation phases, generalized mixed-effects models (GLMM) at patient level with multilevel hierarchical random effects will be developed to analyze the intervention effects on the Without-Fail care rate during the post-implementation period and sustainability period compared with the baseline period.

The baseline data period is the one-year prior to the date of the baseline site visit. The active implementation phase data period extends for one year from month 2-13 after the Kick-Off event. For the primary effectiveness analysis, the main comparison is the mean facility Without-Fail rate across the six sites during the baseline data (control) period (blue shading above) versus the mean facility Without-Fail rate across the six sites during the post-implementation data period including the active implementation and one year after the active implementation phases (green and pink shadings above). We propose to model the “Without-Fail” care rate by

$$\log \frac{P(Y_{ij,k} = 1 | X_{ij,k}, Z_{ij,k}, W_{ij,k})}{1 - P(Y_{ij,k} = 1 | X_{ij,k}, Z_{ij,k}, W_{ij,k})} = \mu + \alpha_i + \beta_j + X_{ij,k}\theta + Z_{ij,k}\gamma + W_{ij,k}^t\tau$$

where i indexes the site ($i = 1, 2, 3, 4, 5, 6$); j the implementation phase (1: baseline period; 2: active implementation phase; 3: one year after the active implementation phase); k the encounter at the i^{th} site and the j^{th} phase ($k = 1, 2, \dots, n_{ij}$); n_{ij} is the total number of encounters at the i^{th} site and the j^{th} phase; $X_{ij,k}$ and $Z_{ij,k}$ the indicators of the active implementation phase and one year after the active implementation phase, respectively; $W_{ij,k}$ the vector of the k^{th} encounter's characteristics at the i^{th} site and the j^{th} phase that could include the site characteristics; $Y_{ij,k} = 1$ the indicator of observation of “Without-Fail” care process on the k^{th} encounter at the i^{th} site and the j^{th} phase. For this model, μ represents the average log odds of Without-Fail care across the 6 sites at baseline; θ the log odds ratio between the active implementation phase and the baseline indicating the intervention effect during the active implementation phase; and γ the log odds ratio between one year after the active implementation phase and the baseline indicating the intervention sustainability effect post the implementation; α_i and β_j are the site and phase specific random effects that are assumed to be multivariate normal. After fitting the model, the normal theory can be applied to test the intervention effect at the active implementation phase and the intervention sustainability effect.

Secondary Aim 2 Analyses: Several secondary effectiveness analyses are planned.

Comparison to Matched Controls

Six control sites will be matched to each of the six PREVENT active implementation sites on the basis of: TIA patient volume, facility complexity (i.e., teaching status, intensive care unit level), and quality of care (measured by the without-fail rate). The total number of control sites will be 36. The definition of the baseline period (the specific start and end dates of the one-year baseline period) for each matched control site will be identical to the definition used for the PREVENT active site to which the controls are matched. We will compare changes in quality and outcomes at control sites to changes at PREVENT sites as a method for assessing temporal trends.

Changes in Individual Processes of Care

An examination of the care rate of facility process for each of the seven primary processes of care across the six sites from the baseline period to post-implementation period will be conducted using the same analytical template as outlined for the primary analysis. A single risk adjustment model will be developed for use in evaluating the seven processes of care and will focus on baseline patient characteristics as follows:

Process	Risk Adjustment Variable
Anticoagulation for atrial fibrillation	Past history of atrial fibrillation (versus new afib)

	Use of anticoagulation prior to index event PMH of GI or intracranial hemorrhage Age Dementia
Antithrombotics	PMH of CAD, MI PMH of diabetes Anti-platelet or anticoagulant prior to index
Brain imaging	PMH of stroke or TIA
Carotid artery imaging	PMH CEA or stent PMH of PVD
High or moderate potency statin	Use of statin prior to index event PMH of CAD, MI PMH of diabetes History of intracranial hemorrhage LDL-cholesterol Age
Hypertension control	Kidney disease, dialysis PMH diabetes PMH of CAD, MI Antihypertensive meds before index event BP before the event and at discharge Homeless PCP visit
Neurology consult	Neurology FTE
General	Hospice, comfort care, AMA Admitted versus ED Transferred into or out of our facility Nights/weekends presentation

90-Day Recurrent Stroke Rate

(1) The 90-Day recurrent stroke rate will be estimated at each site before (baseline and pre-implementation phase) and after (active implementation phase and one year after the active implementation phase) the intervention to examine the temporal trends in intervention effectiveness for reducing the 90-day recurrent stroke rate. The 95% confidence intervals for the rates will be provided.

(2) The similar GLMM at patient level as described for the primary analysis will be developed for the incidence of 90-day recurrent stroke across the six sites and the whole study period to study the mean change of this rate. For this model, the indicator of Without Fail care at the encounter level will be incorporated into the model as the main exploratory variable to examine if the improvement of the Without Fail care rate will result in significant reduction of the 90-Day recurrent stroke rate.

90-Day Mortality

The analysis plan for the 90-day recurrent stroke rate (described above) will also be implemented for the 90-Day Mortality.

Disease-free Survival Analysis

We will examine disease-free survival over the course of 1-year after the index event. We will use Cox proportional hazards modeling, censoring patients for either death or recurrent stroke and examine the relationship between quality of care and disease-free survival.

Temporal Trends in Effectiveness

An examination of the mean Without-Fail rate for the baseline data period through sustainability for all non-participating VA sites with at least 10 TIA patients per year. Given that Indianapolis VAMC has served as the coordinating center, we would not include that site in the analyses.

Consolidated Quality Measure

A consolidated measure of quality defined as the number of passes divided by the number of eligible patients across the seven primary processes of care will be compared for baseline versus post-implementation periods using the same approach described above for the Without-Fail rate analysis.

Secondary Processes of Care

An examination of the secondary processes of care: baseline versus active implementation data periods.

Sensitivity Analyses

The primary analysis will include the first TIA event per patient during the entire study period. In sensitivity analysis, we will include (1) the first event per period and (2) all TIA events in the analysis.

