4.5 Risk Score

As part of the PREVENT program, participating sites are provided with their patient risk score which is a measure of the risk of 1-year mortality. We are interested in two analyses related to the risk score.

1. How did the sites use the patient risk score? This assessment will be based on qualitative interviews with sites at 6-months and 1-year post-implementation.
2. Risk score validation. For this analysis, all VAMCs will be included (not only PREVENT sites). Predicted risk scores, with their 95% confidence intervals, will be compared with observed 1-year mortality and its 95% confidence interval.

TABLE SHELLS

Table 1. Baseline Characteristics: at the Facility-Level

	Baseline (Control)	Pre- Implementation	Post- Implementation (Active Implementation)	Sustainability
Patient Characteristics				
Facility Characteristics				
90-Day Mortality Rate				
90-Day Recurrent Stroke Rate				
90-Day Recurrent TIA Rate				
90-Day Recurrent Stroke or TIA Rate				

Table 2. Unadjusted Effectiveness: at the Facility-Level

THIS IS THE PRIMARY ANALYSIS in terms of the data periods being compared.

	Baseline (Control)	Post- Implementation (Active Implementation)	P- VALUE
Individual Processes of Care			
Anticoagulation for Atrial Fibrillation			
Antithrombotics			
Brain Imaging			
Carotid Artery Imaging			
High/Moderate Potency Statin			
Hypertension Control			
Neurology Consultation			
Mean Facility Consolidated Measure Rate			
Mean Facility Without-Fail Rate			

Table 3. Hierarchical Model: Includes adjustment for patient and facility characteristics

The same approach described for the modelling the without-fail rate can be used to model the outcome rates.

Table 4. Temporal Trends in Quality of Care: Unadjusted

	Baseline (Control)	Pre- Implementation	Post- Implementation (Active Implementation)	Sustainability
Individual Processes of Care				
Anticoagulation for Atrial Fibrillation				
Antithrombotics				
Brain Imaging				
Carotid Artery Imaging				
High/Moderate Potency Statin				
Hypertension Control				
Neurology Consultation				
Mean Facility Consolidated Measure Rate				
Mean Facility Without-Fail Rate				

REFERENCES

1. Williams L. *Stroke Quality Enhancement Research Initiative (QUERI) Strategic Plan and Renewal Report*. 2013.

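### The sentence defining the primary comparison pools the active year with the later phase, while the rest of the plan keeps them apart

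*Combined protocol and SAP*

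**What the plan says.** Section 4.2, Primary Aim 2 Analysis, compares the mean facility Without-Fail rate at baseline with the rate in the "post-implementation data period including the active implementation and one year after the active implementation phases (green and pink shadings above"). Section 4.4 contrasts blue with pink when it compares baseline with sustainability, so pink is the sustainability period.

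Other places treat the two later periods as distinct:

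- **Section 4.2, Effectiveness Data Period Definitions.** The post-implementation column is "1 year after Kick-Off: Months 2-13 after the Kick-Off". Sustainability has its own column: "Variable period: Months 14 after the Kick-Off until 9/30/19".
- **Section 4.2, Descriptive Analysis.** The rate is estimated "for each of the three periods (baseline, post-implementation, and sustainability"). The sentence introducing the mixed model also names the two periods separately.
- **Section 4.2, Power and Sample Size.** The improvement is from 25% at baseline "to >50% during the active implementation data period", and the null hypothesis is θ = 0.
- **Section 2, Secondary Aim.** The contrast is the "rate in the sustainability period to the post-implementation period".
- **Table shells, Table 2.** It carries the label "THIS IS THE PRIMARY ANALYSIS in terms of the data periods being compared", and its only period columns are baseline and post-implementation (active implementation).

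The model in section 4.2 defines θ (active phase versus baseline) and γ (the following year versus baseline). It says both can be tested and does not say which is primary.

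**The concern.** Two places claim to fix the primary data periods, and they disagree. Read literally, the section 4.2 sentence makes the primary result an average of the supported year and the later phase. Table 2 and the power sentence make it the supported year alone. The plan has no rule of precedence, so an analyst could report either as prespecified.

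The literal version has three further problems. No model parameter matches it. The Secondary Aim would compare sustainability with a period that already contains it. And the mix of the two phases would differ by site, because sustainability ends at a common calendar date.

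The plan itself allows for fading: the power section mentions a possible decrement in effect over time, and sustainability is a separate aim. Pooling would blur that distinction. The secondary analyses of individual processes and of the consolidated measure refer back to the primary approach, so they carry some of the ambiguity.

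A related mismatch concerns duration. The Secondary Aim says "Sustainability will be evaluated over a one-year period that begins after the one-year active implementation period", and the model definition also speaks of one year. The tabulated dates do not give a year at every site.

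**Working it through.** **The plan's own power figure.** The plan claims more than 90% power for 25% to above 50%, with 6 sites and at least 30 patients per site-year. With 180 per period and two-sided 0.05 (assumed; the plan states no alpha), a two-proportion normal approximation gives 0.999. A standard stepped-wedge variance (assumed layout: 4 periods, 30 per cluster-period, coefficient of variation 0.2 to 0.8) gives 0.96 to 0.98. The claim holds, but it does not show which comparison was meant.

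**Period lengths** (data-period table, both end dates counted):

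| Site | Active days | Sustainability days | Sustainability share of pooled window |
|---|---|---|---|
| A | 365 | 416 | 416/781 = 0.533 |
| B | 365 | 401 | 401/766 = 0.523 |
| C | 365 | 317 | 317/682 = 0.465 |
| D | 365 | 303 | 303/668 = 0.454 |
| E | 365 | 267 | 267/632 = 0.422 |
| F | 365 | 141 | 141/506 = 0.279 |
| Total | 2,190 | 1,845 | 1,845/4,035 = 0.457 |

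The mean of the six shares is 0.446. Capping each site at 365 days gives 1,758 sustainability days, a site-day share of 0.445 and a mean share of 0.437. Sites C to F have less than a year.

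**Pooled effect.** With a constant encounter rate within site, pooled effect = 25 × (1 − share × fraction lost). The 25 points is the planned 25% to 50%. The fractions lost are assumptions.

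| Weighting | None lost | Half lost | All lost |
|---|---|---|---|
| Equal-weight facility mean (0.446) | 25.0 | 19.4 | 13.9 |
| Site-days (0.457) | 25.0 | 19.3 | 13.6 |
| Equal-weight, capped (0.437) | 25.0 | 19.5 | 14.1 |
| Site-days, capped (0.445) | 25.0 | 19.4 | 13.9 |
| Site A alone (0.533) | 25.0 | 18.3 | 11.7 |
| Site F alone (0.279) | 25.0 | 21.5 | 18.0 |

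**Approximate power.** Sustainability encounters at 30 per site-year: 30 × 1,845/365 ≈ 152, so the pooled group has 180 + 152 = 332. The formula is

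power = Φ{[Δ − 1.96·√(p̄(1−p̄)(1/n₁+1/n₂))] / √(p₁(1−p₁)/n₁ + p₂(1−p₂)/n₂)}.

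For 25% to 40%, active year only: p̄ = 0.325, null SE 0.0494, alternative SE 0.0487, so (0.15 − 0.0968)/0.0487 ≈ 1.09 and power is 0.863.

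| Active-year change | Active year only | Pooled, none lost | Pooled, half lost | Pooled, all lost |
|---|---|---|---|---|
| 25% to 40% | 0.863 | 0.935 | 0.769 | 0.480 |
| 25% to 50% | 0.999 | >0.999 | 0.994 | 0.88 |

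For 25% to 40%, the pooled test falls below the active-year test once about 27% of the effect is lost. With the 365-day cap (144 sustainability encounters) the pooled values in the first row are 0.933, 0.772 and 0.496. This treats encounters as independent and is not the plan's modified formula, so it serves only to compare the two readings.

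**The case against.** The strongest reply is that nobody would fit a pooled effect. The sentence introducing the model takes post-implementation and sustainability each against baseline, the model separates them, and Table 2 says outright which periods are primary. On that view the disputed sentence merely lists the phases that the model then splits. This is a fair softer reading, but it does not settle the matter: the sentence sets one mean rate against another, and the plan never says whether θ alone, or θ and γ together, is primary.

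Some text points towards pooling. The 90-day stroke analysis, and 90-day mortality by reference, uses a combined after-intervention period, though both are secondary outcomes. The power section claims at least 0.90 for an effect of 0.15 with 30 per cluster. On the rough approximation above, the pooled comparison without loss reaches that (0.935) and the active year alone does not (0.863). But the plan's formula is not given and its null hypothesis is on θ, so this is weak evidence of intent.

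It is also true that the loss fractions are assumed, that rates could rise later as well as fall, and that Table 2 already lists the individual processes and the consolidated measure under the active-year column. These points limit the consequences; they do not remove the contradiction.

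**Conclusion.** The concern holds. The sentence defining the main comparison contradicts the data-period table, the descriptive analysis, the power sentence, the Secondary Aim and Table 2. Aim 2 itself conflicts only indirectly, because it gives no dates for the post-implementation phase.

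The pooled contrast equals the active-year effect only if nothing changes afterwards. With a 25-point active-year effect and half or all of it lost, the pooled facility mean would be about 19.4 or 13.9 points. These figures assume a constant encounter rate within site. The primary analysis keeps only each patient's first TIA over the whole study, which would lower later counts by an unknown amount and shrink the sustainability weights.

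Power can move either way for a smaller effect. At the planned effect it stays at 0.88 or above on this approximation, so the main consequence is for what the primary estimate means.

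**What to change.** 1. In the section 4.2 sentence on the main comparison, replace the clause that adds the later phase and the pink shading with: months 2-13 after the Kick-Off (green shading above).
2. Name the test of θ as the single primary test. State at the same point how θ, an adjusted patient-level log odds ratio, relates to the unadjusted facility mean in Table 2, since both cover the same periods.
3. Assign γ (sustainability versus baseline, section 4.4) and γ − θ (sustainability versus post-implementation, section 2) to the Secondary Aim, and say that these are two different contrasts.
4. Where the Secondary Aim, the model definition and the 90-day analyses call the later data period one year, use the tabulated definition: month 14 to 9/30/19, which is 141 to 416 days by site. Reconcile the Design paragraph's sustainability phase of at least a year with that cut-off.
5. The combined after-intervention period for 90-day stroke and mortality can stay if it is labelled as different from the primary comparison.

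This follows the plan's predominant usage. If the sponsor did intend the pooled comparison, the table, the power statement, Table 2 and the model would have to change instead. The recommended change costs wording only: no new data and no additional analysis.
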